6.1.2 Descriptive analyses

Summary statistics will be provided for baseline, as well as for absolute and percent change from baseline in ESSPRI, by treatment and timepoint.

6.1.3 Statistical model, assumptions and hypotheses

It is assumed that the ESSPRI will follow an approximately normal distribution.

A positive sign of therapeutic effects will be considered to be a reduction of at least 1 point in the change from baseline between CDZ173 and placebo with a moderate level of evidence. Additionally there should be a high level of evidence that is a difference between CDZ173 and placebo. These criteria will be evaluated by calculating Bayesian posterior probabilities as follows:

$\Pr(\theta_{\text{CDZ173,13w}} - \theta_{\text{placebo,13w}} < 0 \mid \text{data}) > 90\%$ and

$\Pr(\theta_{\text{CDZ173,13w}} - \theta_{\text{placebo,13w}} < -1 \mid \text{data}) > 50\%$

where θ means change from baseline in ESSPRI at 13 weeks.

It is assumed that Y_{ijt} , the observed change from baseline in ESSPRI for subject i receiving treatment j (CDZ173 or placebo) at time t , follows a normal distribution $N(\theta_{jt}, \sigma^2)$. It is further assumed that θ_{jt} follows a standard non-informative prior Normal distribution, $p(\theta_{jt}, \sigma^2) = 1/\sigma^2$.

The statistical model will be a repeated measures model fitting terms for treatment by timepoint and baseline by timepoint using the SAS procedure PROC MCMC. Estimates of the difference between CDZ173 and placebo at each timepoint will be derived from this model and presented together with 95% credible intervals. The estimates of the posterior probabilities of the efficacy criteria being met will be provided.

Patients with missing ESSPRI at baseline will not be included in the analysis. Patients with missing data at one or more timepoints post baseline will be included in the analysis. The planned model assumes that missing values are missing at random. The reasonableness of this assumption will be checked during the blinded review of the data and if necessary further methods may be applied.

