1.1 Scope of document

The RAP documents contain detailed information to aid the production of Statistics & Programming input into the Clinical Study Report (CSR) for trial “*CCDZ173X2203*”.

The Statistical analysis plan (SAP) describes the implementation of the statistical analysis planned in the protocol.

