6.1.3.2 Handling of missing values/censoring/discontinuations

All subjects with a baseline ESSPRI and at least one post-baseline ESSPRI will be included in the primary analysis. The primary analysis method provides unbiased estimates of the treatment effect under the assumption that data are missing at random (MAR). Guidelines for subject discontinuation should ensure that this assumption is reasonable. If a substantial proportion (e.g. more than 15%) of subjects discontinue before week 13 visit, alternative methods to account for missing data may be considered.

Follow up visits from subjects who discontinued will not be included in the analysis.

For patients where treatment was withdrawn PD summary statistics and all the analysis using the PD analysis set will only include data that was measured ≤ 7 days after the treatment was stopped, i.e. data longer than 7 days after treatment discontinuation will be excluded. For individual figures using the PD analysis set all the data will be displayed but the lines will be solid up to the treatment discontinuation + 7 days and for subsequent time points the line should be dotted, i.e. the data that is excluded from the summary stats/analysis should be presented dotted.

If a subject took a prohibited medication then a footnote will be added to detail this in all PD outputs to explain that data after the usage may be affected by the medication.

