6.1.3.3 Supportive analyses

The supportive analysis will be based on a longitudinal mixed model of change from baseline in ESSPRI as a function of baseline ESSPRI, baseline intake of steroids (yes/no, which is a stratification factor for the randomization), treatment, time (days from first treatment) as a continuous variable (linear and quadratic terms), interaction between treatment and time, as well as a random intercept, random slope and random quadratic effects by subject to account for within-subject correlations.

An unstructured covariance matrix for the random effects will be fitted along with an independent error matrix. The difference between active treatment and placebo in change from baseline in ESSPRI at study week 13 will be estimated from the model and presented with 80% and 95% confidence intervals (estimates will also be provided corresponding to the other visits where ESSPRI was assessed). Simpler models will also be considered in case the pre-specified model does not fit the data well.

Simpler models may be considered, including simpler covariance structures. If the time course does not appear to be quadratic, time may be modelled as a categorical variable.

The following criteria will be considered indicative of treatment efficacy:

- Statistically significant decrease in ESSPRI at week 13 visit on treatment compared to placebo (at one-sided 10% level)
- Estimated mean reduction in ESSPRI at week 13 visit for CDZ173 of 1 point or more than for placebo

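### The SAP's primary ESSPRI model leaves out the only randomisation stratum and states no within-patient covariance or prior for one, so its missing-at-random sentence is not tied to a stated likelihood

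*SAP*

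**What the plan says.** **Primary model (SAP 6.1.3).** Change from baseline in ESSPRI is normal with a mean indexed by treatment and time and a variance σ² with no time index. The prior is called a "standard non-informative prior Normal distribution" and is written for the mean and σ² only, as 1/σ². The analysis is a "repeated measures model fitting terms for treatment by timepoint and baseline by timepoint using the SAS procedure PROC MCMC". Success needs a posterior probability above 90% that the week-13 difference is below 0, and above 50% that it is below −1.

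**Protocol 11.4.2.** The primary model there has baseline ESSPRI, baseline steroid intake (named as the stratification factor), treatment, linear and quadratic time, treatment by time, and three random effects per patient. SAP 6.1.3.3 keeps this model as supportive and does state its covariance: "An unstructured covariance matrix for the random effects will be fitted along with an independent error matrix".

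**Missing data.** SAP 6.1.3.2 repeats a sentence from protocol 11.4.3: "The primary analysis method provides unbiased estimates of the treatment effect under the assumption that data are missing at random (MAR". For patients who stop treatment, "data longer than 7 days after treatment discontinuation will be excluded". Two safeguards follow. On missing at random, 6.1.3 says: "The reasonableness of this assumption will be checked during the blinded review of the data and if necessary further methods may be applied". Above about 15% discontinuation, 6.1.3.2 says that "alternative methods to account for missing data may be considered".

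**Role of the SAP.** Section 1.1 refers to RAP documents in the plural, but it is the SAP that "describes the implementation of the statistical analysis planned in the protocol".

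**The concern.** PROC MCMC has no default covariance for repeated visits, so the programmer must write the likelihood and every prior. Independent visits and a random patient intercept can both be coded from this text, and they need not give the same week-13 posterior. Both efficacy criteria are read from that posterior.

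The missing-data assurance depends on the same choice. A joint likelihood that models the correlation uses a drop-out's earlier ESSPRI, so it is valid when missingness depends on observed earlier values. A likelihood with independent visits estimates week 13 only from patients seen at week 13. It is then safe only when missingness depends on treatment and baseline.

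The stratum is a separate matter. Randomisation balances steroid use between arms either way, but leaving the term out keeps any steroid-related variation in the residual.

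**Working it through.** **1. The protocol's own figure.** Inputs from protocol 11.6: 16 against 8 patients, SD 2, true difference 2, both criteria, one-sided 10%.

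- SE = 2 × √(1/16 + 1/8) = 2 × 0.433 = 0.866.
- Significance cut-off = 1.2816 × 0.866 = 1.11, already beyond 1 point.
- Power = Φ((2 − 1.11)/0.866) = 84.8%; false positives 10.0%.
- With the SD estimated (t, 22 df) and both criteria applied, simulation gives 83.3% and 9.5%.

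The protocol states 86% and around 10%, so its figures are reproduced to within 3 points.

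**2. What is stated for each model.**

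| Item | Protocol primary | SAP primary | SAP supportive |
|---|---|---|---|
| Steroid stratum | yes | no | yes |
| Within-patient covariance | random effects, unstructured | not stated | random effects, unstructured |
| Prior for covariance | not needed | not stated | not needed |

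No redaction mark falls in SAP 6.1.3 to 6.1.3.3.

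**3. Stratum.** Assume half the patients use steroids, a steroid gap of g points and a total SD of 2. The stratum then accounts for g²/4 of a variance of 4:

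- g = 0.5: 0.0625/4 = 1.6%
- g = 1: 0.25/4 = 6.25%
- g = 2: 1/4 = 25%

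In simulation at a true difference of 2 points, adding the stratum changes power by about nil for a gap of 0 to 0.5 points, +1 point at a 1-point gap and +3 points at a 2-point gap. For 1- and 2-point gaps the mean estimate is −2.00 with or without the term.

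**4. One variance for all visits.** Assume independent coding, complete data, 16/8 patients and correlation 0.7. Under the flat prior the 90% criterion is met when the estimate lies below −t × SE, with SE taken from the variance pooled over visits.

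- SDs 2/2/2 at weeks 5/9/13: false positives 9.6% to 10.1% in separate runs.
- SDs 1.4/1.7/2: mean variance = (1.96 + 2.89 + 4)/3 = 2.95, SD 1.72. The cut-off becomes 1.2816 × 1.72 × 0.433 = 0.95, so the 1-point criterion takes over. The rate is then at most Φ(−1/0.866) = 12.4%; simulated 11.9% to 12.1%.
- SDs 2.3/2.15/2: 8.4%.

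Only the SD of 2 comes from the documents.

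**5. Drop-out.** Assumed: 18/9 patients, about 10% missing at week 13, correlation 0.7, and an effect reaching 50%, 75% and 100% of its week-13 value at weeks 5, 9 and 13. Outcome-dependent drop-out follows the last ESSPRI change at one logit per point. There are 4,000 trials per row.

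| Missingness | True difference | Mean: independent / random intercept | Both criteria met |
|---|---|---|---|
| Completely at random | 0 | no shift in either | 10.4 / 9.6% |
| Baseline and arm only | 0 | 0.02 or less in either | 10.6 / 9.9% |
| Last change, same rule in both arms | −2 | −1.80 / −1.97 | 78.2 / 81.7% |
| Last change, active arm only | 0 | −0.28 / 0.02 | 16.6 / 9.4% |
| Last change, placebo only (31% of placebo missing) | 0 | +0.60 / 0.02 | 2.0 / 9.0% |

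The same rule in both arms with no treatment effect gives no shift. At 0.25 logit per point the one-arm shifts shrink to −0.08 (false positives 11.4%) and +0.21. An unstructured covariance removes the shifts as the random intercept does.

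**6. Prior for the covariance.** For a 3 × 3 inverse-Wishart with 4 degrees of freedom and scale sI, the week-13 variance has 4 − 2 = 2 degrees of freedom and variance scale s/2. Matching the protocol's SD of 2 needs s/2 = 4, so s = 8. Scale 4I looks natural but centres on 2, an SD of 1.4. With n = 24 and four coefficients at week 13, the posterior t has 24 − 4 + 4 − 2 = 22 df. Under |Σ|⁻² it has 24 − 4 − 2 = 18.

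**The case against.** The strongest reply is that the drop-out shifts all need one coding, independent visits, and the repeated measures label argues against it. A reader might infer from the displayed formula that the SAP intends independence, and hence that its primary estimate is biased and its missing-at-random sentence false. The documents do not support that. The formula is schematic: it also omits the baseline term that the next paragraph includes. By the same reasoning the missing visit index on σ² may be shorthand. The missing-data sentence would be correct for a properly specified joint likelihood. What stands is that the structure is unstated, not that it is wrong.

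The supportive model is a second fair point. It has the stratum and the random effects, reports 80% and 95% intervals, and applies its own pair of efficacy criteria at week 13. A shift from ignored correlation would show as disagreement with it. This mitigates in part, since the SAP does not say what follows if the two disagree. The other safeguards are discretionary, a blinded review cannot compare missingness by arm, and the 15% trigger lies above the 10% missing used here.

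On the stratum, the protocol's background calls glucocorticoids ineffective in this disease, and oral doses must be low and stable. A 2-point gap would equal the whole effect the trial is powered for, and no gap is given anywhere. A gain of nil to 1 point is the more cautious expectation. A reader might also infer that omission biases the comparison; it does not.

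Finally, the trial is non-confirmatory. That lowers the stakes but does not remove the need for one defined primary analysis.

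**Conclusion.** The point holds as a gap in specification, minor to should-fix. The omitted stratum and the unstated covariance and prior can be read directly from the text. The consequences are conditional: steroid gaps, visit SDs, the correlation of 0.7 and the drop-out rules are all assumed.

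The amount missing at week 13 cannot be worked out either. Data beyond 7 days after a treatment stop are excluded, protocol 11.6 does not say whether its 10% drop-out counts such stops, and protocol 7.5 allows replacement. At the only SD the documents give, with complete data, even the least favourable coding keeps false positives near 10%. Material shifts need both independent coding and drop-out that follows earlier ESSPRI and acts unevenly between arms.

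**What to change.** Amend the SAP before database lock:

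1. In 6.1.3, add baseline steroid intake (yes/no) to the primary model, and say whether it enters as one term, as in the protocol, or by timepoint.
2. Write the likelihood as multivariate normal over weeks 5, 9 and 13 (the post-baseline on-treatment ESSPRI visits in protocol Table 8-1), with visit-specific variances and an unstructured within-patient covariance. Fix its prior, for example inverse-Wishart with 4 degrees of freedom and scale 8I, and name other priors, such as |Σ|⁻², as sensitivity analyses.
3. In 6.1.3.2, tie the missing-at-random sentence to that model.

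This needs SAP wording, a few lines of code and one degree of freedom at week 13, and no new data. With complete data, no steroid gap and a true difference of 2 points, simulated power is about 82.0% with the scale-8I prior, against 82.9% for independent visits without the stratum. Under |Σ|⁻² it is about 80%. The cost therefore runs from about 1 to 3 power points, depending on the prior, which is why the prior has to be fixed in advance.

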Treatment for pSS patients is limited to symptomatic care for the mucosal signs and symptoms. Glucocorticoids and typical disease-modifying anti-rheumatic drugs (DMARDs) are ineffective, and no pharmacologic intervention is effective against the severe, disabling fatigue. Although small trials with the B cell depleting agent rituximab have demonstrated a degree of therapeutic efficacy in approximately 50% of pSS patients, no proper, large randomized controlled trials have shown clear efficacy in pSS. Thus, a disease modifying agent that prevents secretory gland destruction and addresses extra-glandular disease manifestations would introduce a significant advance for the treatment of pSS.

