3.2 Rationale of study design

CDZ173 is an oral, low molecular weight compound that selectively inhibits the lipid kinase PI3K δ , an important mediator of immune cell activation and germinal center formation. The essential role of PI3K δ in the adaptive as well as the innate immune system strongly supports the rationale for the PI3K δ targeted intervention in autoimmune diseases. The interference with germinal center formation further supports expected efficacy in patients with pSS where ectopic germinal centers in salivary glands are considered pathogenically important. This study will be conducted in patients with active pSS, where no established clinically effective disease modifying treatment has been proven effective against the underlying disease.

A randomized, placebo-controlled, double-blind approach is used to eliminate potential bias in reporting safety and clinical efficacy data. Patients will be randomized to CDZ173 or placebo in a 2:1 ratio in order to minimize exposure to placebo and to gather more data on CDZ173. Stratified randomization is done in order to limit imbalances between active and placebo arms in baseline intake of oral corticosteroids.

After the double-blind period, the patients will enter a follow-up period; for which a duration of 4 weeks was chosen to allow sufficient time for safety monitoring.

In addition to safety, efficacy estimated by the EULAR Sjögren's Syndrome Patient Reported Index (ESSPRI) is chosen as a key endpoint of the study (Seror et al 2011). A decrease of 1.7 points was observed at week 16 in a small open-label study with rituximab (Meiners et al 2012). In a publication the group of Seror reported 0.67 – 1 ESSPRI points to be the minimal clinically important improvement (Seror et al 2016). In addition to the ESSPRI, efficacy estimated by the EULAR Sjögren's Syndrome Disease Activity Index (ESSDAI) is chosen as a second disease specific endpoint of the study. The ESSDAI assesses organ involvement in patients with pSS and has been shown to be sensitive to suggest efficacy of rituximab treatment in a randomized controlled trial (Moerman et al 2014). Further efficacy assessments include diseases-independent outcome variables (SF-36, MFI, patients' and

physicians' global assessments)

Corporate Confidential Information

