6.4 Treatment assignment and randomization

At Baseline/Randomization visit, all eligible subjects will be randomized via Interactive Response Technology (IRT) to one of the treatment arms. The investigator or his/her delegate will contact the IRT after confirming that the patient fulfills all the inclusion/exclusion criteria. The IRT will assign a randomization number to the patient, which will be used to link the patient to a treatment arm and will specify a unique medication number for the package of study drug to be dispensed to the patient. The randomization number will not be communicated to the caller.

The randomization numbers will be generated using the following procedure to ensure that treatment assignment is unbiased and concealed from patients/subjects and investigator staff. A patient randomization list will be produced by the IRT provider using a validated system that automates the random assignment of patient numbers to randomization numbers. These randomization numbers are linked to the different treatment arms, which in turn are linked to medication numbers. A separate medication list will be produced by or under the responsibility of Novartis Drug Supply Management using a validated system that automates the random assignment of medication numbers to packs containing the investigational drug(s).

Randomization will be stratified by use of corticosteroids (yes/no). The randomization scheme for patients will be reviewed and approved by a member of the Randomization Office.

Follow the details outlined in the Site Operations Manual regarding the process and timing of treatment assignment and randomization of patients.

The investigator will enter the screening number and medication number in the eCRF.

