11.4.2 Statistical model, hypothesis, and method of analysis

It is assumed that the ESSPRI will follow an approximately normal distribution. If this assumption appears not to be met, alternative statistical analysis methods may be applied. These will be described in the Reporting and Analysis Plan (RAP).

The primary efficacy analysis will be based on a longitudinal mixed model of ESSPRI as a function of baseline ESSPRI, baseline intake of steroids (yes/no, which is a stratification factor for the randomization), treatment, time as a continuous variable (linear and quadratic terms), interaction between treatment and time, as well as a random intercept, random slope and random quadratic effects by subject to account for within-subject correlations. An unstructured covariance matrix for the random effects will be fitted along with an independent error matrix. The difference between active treatment and placebo in change from baseline in ESSPRI at study week 13 will be estimated from the model and presented with 80% confidence intervals. Simpler models will also be considered in case the pre-specified model does not fit the data well.

The following criteria will be considered indicative of treatment efficacy:

- Statistically significant decrease in ESSPRI at week 13 visit on treatment compared to placebo (at one-sided 10% level)
- Estimated mean reduction in ESSPRI at week 13 visit of 1 point or more than on placebo (see [Section 3.2](#))

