11.6 Sample size calculation

A total of approximately 27 patients will be recruited into the study. Patients will be randomized in a 2:1 ratio to either CDZ173 (n=18) or placebo (n=9) treatment groups. This number is based firstly on the assumed treatment effect in the primary endpoint ESSPRI and secondly on an assumed drop-out rate of 10% (i.e. 3 patients).

With 24 patients for the analysis of the primary efficacy variable (16 in the CDZ173 treated group and 8 in the placebo group), the study would have around 10% chance of having a false-positive result, i.e. of meeting both efficacy criteria when the true difference between CDZ173 and placebo is zero ESSPRI points.

The power of the study is 86% (when the true difference between CDZ173 and placebo is 2 points in ESSPRI).

The criteria for success are assumed to be the efficacy criteria defined in [Section 11.4.2](#).

These calculations assume that the change from baseline in ESSPRI is approximately normally distributed with a standard deviation of 2. This estimate of the standard deviation is based on a study of rituximab in patients with pSS ([Meiners et al 2012](#)).

The calculated numbers come from simulations done in R version 3.2.2.

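### The SAP's primary Bayesian model omits baseline corticosteroid use, the randomisation stratification factor that the protocol's primary model adjusts for; restoring it would give a small gain in precision if steroid use is prognostic

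*SAP*

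**What the plan says.** Protocol 3.2 gives the purpose of the stratification: "Stratified randomization is done in order to limit imbalances between active and placebo arms in baseline intake of oral corticosteroids". Sections 3.1, 6.2 and 6.4 repeat that steroid use (yes/no) is the stratifier. The primary model in Protocol 11.4.2 carries the factor through to the analysis; after baseline ESSPRI it lists "baseline intake of steroids (yes/no, which is a stratification factor for the randomization), treatment, time as a continuous variable".

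SAP 1.1 presents the SAP as implementing the protocol's analysis. For the primary ESSPRI analysis, however, SAP 6.1.3 specifies a "repeated measures model fitting terms for treatment by timepoint and baseline by timepoint using the SAS procedure PROC MCMC". Two posterior probabilities from that model define a positive sign of effect at week 13: above 90% that the difference is below 0, and above 50% that it is below -1. Steroid intake is not among the terms.

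The factor survives in SAP 6.1.3.3, where the supportive analysis is a "longitudinal mixed model of change from baseline in ESSPRI as a function of baseline ESSPRI, baseline intake of steroids" and other terms, with the protocol's two efficacy criteria attached.

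**The concern.** When randomisation is balanced within strata, the treatment estimate already benefits: differences between strata largely cancel between arms. A model without the stratum term does not credit this. It leaves the between-stratum variance in the residual, so the posterior is wider than the estimate's real sampling variability.

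The result is not bias. It is a conservative first criterion (posterior probability above 90%) and some lost chance of a positive readout when the drug works. With 24 patients planned for analysis, a gain that needs no extra patients or data is worth taking. There is also an unexplained departure from the protocol in the analysis that decides success.

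**Working it through.** **Inputs from the documents.** Protocol 11.6 gives 24 analysed patients (16 CDZ173, 8 placebo), a true difference of 2 points, power of 86%, a false-positive rate of around 10%, and the assumption that "the change from baseline in ESSPRI is approximately normally distributed with a standard deviation of 2". Protocol 11.4.2 gives the criteria: one-sided 10% significance and an estimated difference of at least 1 point.

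**Assumed, because the documents give no figures.** Number of steroid users (9 of 24, varied over 3, 6 and 12), split 2:1 between arms; gap between strata in mean ESSPRI change (0 to 2 points).

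**Step 1: the plan's own power.** SE = 2 × √(1/16 + 1/8) = 0.866. By the normal approximation the significance threshold is 1.2816 × 0.866 = 1.11 points, and power = Φ(2/0.866 − 1.2816) = 84.8%. The 1-point criterion adds nothing, since 1.11 already exceeds 1. With a t distribution on 22 df, joint power is 83.3% and the joint false-positive rate 9.4%. The stated 86% and 10% are reproduced to within 1.2 to 2.7 points and 0.6 points.

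**Step 2: the SAP criteria at week 13.** Under the non-informative prior, the posterior of the difference in a single-visit comparison is a t distribution. Criterion 1 is then the one-sided 10% t-test, and criterion 2 is an estimate below −1. The steroid term takes one df (22 to 21).

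**Step 3: how much too wide the posterior is.** With p = 9/24, p(1−p) = 0.234. Holding total variance at 4, within-stratum variance is 4 − 0.234 × gap². The unadjusted residual variance is within-stratum variance + 24 × 0.234 × gap²/22. At a gap of 2:

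- within-stratum variance = 4 − 0.9375 = 3.0625
- residual variance = 3.0625 + 22.5/22 = 4.085
- excess width = √(4.085/3.0625) = 1.155, about 15%

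In simulation at this gap, the model SE is 0.866 without the term while the estimate's true SD is 0.76.

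**Step 4: simulation.** 200,000 trials per setting, week 13 only, both criteria required, 9 users.

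| Gap (points) | Joint power, without → with term (%) | Joint false-positive rate, without → with (%) | Posterior SD too wide by |
|---|---|---|---|
| 0 | 83.3 → 83.3 | 9.4 → 9.4 | 0% |
| 0.5 | 83.5 → 83.6 | 9.3 → 9.4 | 1% |
| 1 | 83.9 → 84.8 | 8.8 → 9.3 | 3% |
| 1.5 | 84.8 → 86.6 | 7.8 → 8.9 | 8% |
| 2 | 86.1 → 89.1 | 6.6 → 8.3 | 15% |

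Power without the term also rises with the gap, because total SD is held at 2 and stratification removes part of it from the estimate.

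**Step 5: sensitivity.** Power gain in points at gaps 1 / 1.5 / 2:

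| Setting | Gain |
|---|---|
| 3 users | +0.3 / +0.9 / +1.6 |
| 6 users | +0.7 / +1.5 / +2.5 |
| 12 users | +0.8 / +2.0 / +3.2 |
| Baseline ESSPRI in both models (assumed SD 1.5, correlation with change −0.3), unrelated to steroid use | +0.8 / +1.8 / +2.9 |
| Same, baseline–steroid correlation −0.3 | +0.1 / +0.9 / +1.7 |
| Same, baseline–steroid correlation +0.3 | +1.5 / +3.0 / +4.4 |

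If the planning SD of 2 is a within-stratum SD (9 users), power without the term falls to 83.1 / 82.3 / 81.2 / 79.5% at gaps 0.5 / 1 / 1.5 / 2; with the term it stays at about 83%.

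A separate simulation used permuted blocks of 3 (assumed) within strata and 20% steroid users. If steroid use explains 5, 10 or 20% of outcome variance, power goes from 83.7 to 84.3%, 84.3 to 85.6% and 85.4 to 88.3%.

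**Step 6: cost if steroid use is not prognostic.** An exact 2:1 split of users costs at most 0.1 point of power, and blocked randomisation about 0.2 to 0.3. Particular unlucky splits (active:placebo) cost more: 0.9 points at 5:4 or 7:2, and 2.0 at 3:0.

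**The case against.** The strongest reply is that little turns on this. The study is non-confirmatory, and SAP 6.1.3.3 already pre-specifies an adjusted analysis with 80% and 95% intervals and the protocol's two criteria. Nothing in the documents shows steroid use to be prognostic. The outcome is change with baseline ESSPRI already in the model, entry steroid doses are capped and must be stable, and Protocol 1.1 states: "Glucocorticoids and typical disease-modifying anti-rheumatic drugs (DMARDs) are ineffective". Gains above 1 to 2 points need a stratum gap of 1.5 to 2 points, beyond the 0.67 to 1 point that the protocol cites as the minimal clinically important improvement.

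Much of this stands: the gain may be near nil and an adjusted readout will exist. But ineffectiveness as a treatment does not settle prognosis, since steroid users may differ in disease course whether or not steroids help. The supportive model also differs in its time structure, random effects and inferential framework, so it neither supplies the two posterior probabilities nor isolates the effect of the steroid term.

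The objection that the term is not strictly free is also fair (Step 6). Yet in the unbalanced splits where it costs 1 to 2 points, a 1-point gap would move the unadjusted false-positive rate to about 6% or 13%, depending on direction, while the adjusted rate stays near 9.4%.

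Finally, parts of the SAP are redacted or removed, so the absence of a reason can be asserted only for the readable text.

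**Conclusion.** The concern holds as an optional improvement. The omission from the primary model is certain on the text; its size is not. Under the stated assumptions the term adds about 1 point of joint power at a 1-point gap and about 3 points at a 2-point gap, and it brings the false-positive rate closer to the planned 10%. With no steroid effect it gives no gain and a small average cost. There is no bias from leaving it out. Power falls below its no-gap value only if the planning SD of 2 is a within-stratum SD.

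The figures rest on assumed shares of users, gaps and correlations, and on a week-13 comparison. Earlier visits, missing data and the full repeated-measures structure were not simulated.

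**What to change.** Add baseline steroid intake (yes/no) by timepoint to the mean model in SAP 6.1.3, so that the two posterior probabilities are computed with it, using the coding already set in SAP 6.1.3.3. The by-timepoint form matches the other terms of the Bayesian model; the protocol lists the factor without a time interaction. If the sponsor prefers to leave the factor out, the SAP should say why. Either change should be made before database lock.

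The cost is three coefficients, one for each on-treatment ESSPRI visit (weeks 5, 9 and 13), and no new data or patients.
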